7.2 Visit 2 – Index Procedure

- Targeted Physical Exam (prior to Index Procedure)
- Vital Signs (prior to Index Procedure)
- VAS (prior to Index Procedure)
- Index Procedure (Study Arm - Intercostal Analgesia or Control Arm – SOC Pain Management)
- Concomitant Procedure Type
- Concomitant Medication Review
- Adverse Events Assessment
- Date and Time Subject Exits Surgical Suite

7.3 Visit 3 24 hour Post-Operative Follow-Up Visit

- Vital Signs
- Concomitant Medication Review
- Adverse Event Assessment

7.4 4, 5, 6 and 7 – 48, 72, 96 and 120 Hour Post-Operative Follow-up Visits

- Vital Signs
- Spirometry
- VAS
- Ambulatory Movement
- Concomitant Medication Review
- Adverse Events Assessment

7.5 Visit 8 – Hospital Discharge

- Vital Signs
- Spirometry
- VAS
- Ambulatory Movement
- Concomitant Medication Review
- Adverse Events Assessment
- Date and Time of Discharge from ICU
- Date and Time of Extubation
 - Extubation is anticipated to occur during the first 24 - 36 hours post-op but may occur at any time during hospital stay.
- Date and Time of Hospital Discharge

7.6 Visit 9 – 30 Day Post-Operative Follow-Up Visit

- Vital Signs
- Spirometry
- Concomitant Medication Review
- Adverse Events Assessment

7.7 Visit 10 – 90 Day Post-Operative Follow-Up Visit (Phone call)

- Vital Signs required if subject is seen in the office for allodynia assessment
- Allodynia Screening
- Concomitant Medication Review
- Adverse Events Assessment

7.8 Visit 11 – 180 Day Post-Operative Follow-Up Visit (Phone call)

- Vital Signs required if subject is seen in the office for allodynia assessment

- Allodynia Screening
- Concomitant Medication Review
- Adverse Events Assessment
- Study Exit (See 7.9)

7.9 Study Exit

At study exit the following must be collected.

- Study Exit Date
- Exit Reason

7.10 Allodynia Visits

Allodynia screening questions will be included at the 90 and 180 day visits. If the questions elicit a positive response, the subjects will be asked to make an office visit for a more thorough allodynia assessment. Vital signs will be collected along with the allodynia assessment.

7.11 Repeated Study Visit Tests

All study procedures should be conducted at the investigational site.

Targeted Physical Examination: A targeted physical exam (PE) includes an assessment of the following body systems: General Appearance, Cardiovascular, Respiratory, and Musculoskeletal. A more thorough PE may be conducted according to institutional SOC. If any findings are noted during the PE, the finding should be recorded in the source documents as medical history or as an adverse event, as appropriate. The finding shall be recorded in the eCRF as required per the Safety section of the protocol.

Vital Signs: Vital signs should be taken in accordance with institutional SOC and include pulse rate, blood pressure, temperature and respiration rate.

Height/Weight: Height and weight should be taken in accordance with institutional SOC. BMI will be calculated automatically by the EDC based on the height and weight taken at Visit 1.

Spirometry: Spirometry assessments including: forced expiratory volume (FEV₁) forced vital capacity (FVC) and slow vital capacity (SVC). To allow for consistency across study sites, these spirometry measurements will be captured on a commercially available bedside device provided by AtriCure.

Ambulatory movement: Ambulatory movement assessed by "Yes- Independently", "No" or "Yes - with assistance" responses to the following questions:

- Is patient able to sit up in bed?
- Is patient able to stand up?
- Is patient able to walk?

Ambulatory movement will also be assessed via "shoulder flexion movement" of "Limited ROM", "Full ROM" or "Unable". Ambulatory movement will be collected individually for each shoulder.

Visual Analog Scale (VAS): The Visual Analogue Scale and Mankoski Pain Scale Definitions are found in Appendix 1. The subject should be asked to complete the scale to rate their current pain level for general pain intensity. In addition, the subject should be asked to complete the scale to rate their current pain level for pain intensity related to the surgical region. The person conducting the test at the site should be blinded as to treatment group.

Concomitant Medication Review: All medications, including vitamins or nutritional supplements currently prescribed to, or taken by, the subject shall be recorded in the subject's source documents. Only medications taken for pain management therapy need to be reported on the eCRFs.

Adverse Event Assessment: All adverse events shall be recorded in the subject's source documents. Only adverse events that are related to the intercostal analgesia procedure or the AtriCure® cryoICE cryo-ablation system need to be reported on the eCRFs. Refer to description of collection of Adverse Events for additional information.

Allodynia Screening: As part of the 90 and 180 day follow-up visit, a series of questions will be asked of the subject to determine if an in-office visit is necessary to further evaluate the presence of allodynia.

Allodynia Assessment: Cotton Tip Applicator (CTA) Test. See Appendix 2 for instructions. The same person at the site should administer the test at each time point and should be blinded as to treatment group.

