I will ensure that the IRB review complies with governmental requirements and will be responsible for the initial and continuing review and approval of the clinical investigation. I also agree to promptly report to the IRB all changes in the research activity and all unanticipated problems involving risks to human subjects or others. Additionally, I will not make any changes in the research without sponsor and IRB approval of an amended protocol, except where necessary to eliminate apparent immediate hazards to human subjects.

I agree to comply with all other requirements regarding the obligation of clinical investigators and all other pertinent requirements of the sponsor and government agencies.

Investigator Signature: I have read and understood the contents of this protocol. I agree to follow and abide by the guidelines set forth in this document.

Signature of Principal Investigator

Date

Printed Name of Principal Investigator

[figure not shown]
Please scan, email or fax this signed page to:

PLEASE RETAIN THE ORIGINAL IN YOUR STUDY RECORDS.

SPONSOR SIGNATURES

Protocol Name:	cryoICE™ CryoAnalgesia Study
Protocol Number:	CP2015-4
Protocol Title:	The cryoICE™ CryoAnalgesia study For pain management in post tho R acic procedures via interc O STal cryoanalgesia (FROST)
Name of Finished Product(s):	The AtriCure® cryoICE cryo-ablation system [REDACTED] [REDACTED]

Approvals:

CLINICAL STUDY PROTOCOL SYNOPSIS

Protocol Name:	cryoICE™ CryoAnalgesia Study
Protocol Number:	CP2015-4
Protocol Title:	The cryoICE™ CryoAnalgesia study For pain management in post thoRacic procedures via intercOSTal cryoanalgesia (FROST)
Name of Finished Product(s):	The AtriCure® cryoICE cryo-ablation syste [REDACTED]
Development Phase:	Exempt, post market
Study Design:	This is a prospective, multicenter, randomized (3:1), blinded study

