3.0 STUDY ENDPOINTS

The following endpoints will be collected for this study:

Co-Primary Endpoints:

[figure not shown]
1. Forced Expiratory Volume (FEV₁) at 48-hours post-surgery
2. Visual Analogue Scale (VAS) pain in the surgical region at 48-hours post-operative

Secondary Endpoints:

1. Spirometry assessments including: forced expiratory volume (FEV₁), forced vital capacity (FVC) and slow vital capacity (SVC) at 48-hours post-extubation and other designated time points during hospital admission
2. Pain in the surgical region assessed via a Visual Analogue Scale (VAS) pain at 72-, 96- and 120-hours (as long as patient remains in hospital up to 120-hours) post-operative
3. Allodynia at 3 and 6 months
4. Duration of oral endotracheal intubation defined as hours until patient is extubated from time patient leaves the operating room
5. Patient Controlled Analgesia (PCA) and oral opioid consumption up to each time point (24-, 48, - 96 and 120-hours) and total PCA and oral opioid consumption after extubation
6. ICU length of stay and hospital length of stay
7. Ambulatory movement

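### Section 7.11 asks for blinded testers for VAS and allodynia but not for spirometry or ambulatory movement, so co-primary FEV1 at 48 h may be collected by staff who know the arm

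*Combined protocol and SAP*

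**What the plan says.** The synopsis describes the design in one line: "This is a prospective, multicenter, randomized (3:1), blinded study". Neither it nor sections 4.1 and 9.4 say who is blinded. Sections 4.1 and 9.4 say only that a sealed envelope is opened before the procedure to show the arm.

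Section 3.0 (repeated in 9.2) names two co-primary endpoints: "Forced Expiratory Volume (FEV₁) at 48-hours post-surgery" and "Visual Analogue Scale (VAS) pain in the surgical region at 48-hours post-operative".

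Section 7.11 then describes each assessment:

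- **VAS.** The patient does the rating: "the subject should be asked to complete the scale to rate their current pain level for pain intensity related to the surgical region". On the tester: "The person conducting the test at the site should be blinded as to treatment group".
- **Allodynia (cotton tip applicator test).** "The same person at the site should administer the test at each time point and should be blinded as to treatment group".
- **Spirometry.** Apart from naming FEV1, FVC and SVC, the paragraph says only: "To allow for consistency across study sites, these spirometry measurements will be captured on a commercially available bedside device provided by AtriCure".
- **Ambulatory movement.** The questions and response categories are given, with nothing about the assessor.

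Sections 7.4 and 7.5 list spirometry, VAS and ambulatory movement together at the 48, 72, 96 and 120 hour visits and at discharge. Section 7.6 lists spirometry at 30 days, without VAS.

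**The concern.** The protocol recognises that a tester who knows the arm can influence a result, and guards against it for one co-primary (VAS) and one secondary endpoint (allodynia). It is silent for the other co-primary.

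The spirometry provision concerns equipment. A common device makes readings comparable between sites, but it does not control how an operator instructs or encourages a patient who has just had a thoracotomy. That forced expiratory measures respond to effort and coaching is general knowledge of spirometry and is not stated in the protocol. If it is accepted, an operator who expects the cryoanalgesia patients to do better could shift FEV1 in one arm without intending to.

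Such a shift would add directly to the estimated treatment difference. A larger sample would not remove it, and neither would the t-test planned in section 9.6.1. The ambulatory movement assessment, a secondary endpoint, has the same gap.

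**Working it through.** **Comparison of the text**

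| Assessment (section 7.11) | Endpoint status | Blinded-tester rule |
|---|---|---|
| VAS, surgical region | Co-primary at 48 h; secondary later | Yes (worded as should) |
| Cotton tip applicator test | Secondary (allodynia) | Yes (worded as should) |
| Spirometry | FEV1 co-primary at 48 h; others secondary | None |
| Ambulatory movement | Secondary | None |

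The VAS sentence cannot easily be read as covering every test. It sits inside the VAS paragraph and refers to a single test, and the allodynia paragraph needed a blinding sentence of its own.

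**Inputs for the illustration.** Section 9.3 gives 75 and 25 subjects, an FEV1 difference of 0.26 (control mean 1.3), SD 0.39, and a two-sided equal-variance t-test at 0.05. Section 9.3 prints no unit for FEV1; litres are assumed here. The size of any measurement shift is not in the documents and is assumed.

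**Step 1: reproduce the plan's power.**

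SE = 0.39 × √(1/75 + 1/25) = 0.0901. Degrees of freedom = 75 + 25 − 2 = 98, critical t = 1.984.

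Noncentrality = 0.26 / 0.0901 = 2.89. Power from the noncentral t = 81.6%, against the stated 80%.

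For VAS (difference 1.8, SD 2.2): SE = 2.2 × √(1/75 + 1/25) = 0.508, noncentrality = 3.54, power = 93.9%, against the stated 94%. The method agrees with the plan to within 2 percentage points.

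**Step 2: set the true FEV1 effect to zero and add a shift b to one arm only.**

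Noncentrality = b / 0.0901. The rejection probability is P(|T| > 1.984), where T is noncentral t with 98 df.

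| Assumed shift b | Share of planned 0.26 | Noncentrality | False-positive rate |
|---|---|---|---|
| 0 | 0% | 0 | 5.0% |
| 0.02 L | 8% | 0.22 | 5.6% |
| 0.03 L | 12% | 0.33 | 6.3% |
| 0.065 L | 25% | 0.72 | 11.0% |
| 0.10 L | 38% | 1.11 | 19.6% |
| 0.13 L | 50% | 1.44 | 29.8% |

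These rates are for the FEV1 test alone, not for the pair of co-primaries. They assume that the shift runs the same way, on average, across all sites.

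**The case against.** **The text permits unblinded FEV1 collection but does not prescribe it.** Spirometry and VAS fall at the same in-hospital visits, and the study is labelled blinded. Sites might well use one blinded tester for both. This stands, and the point is therefore about what the plan leaves open. Nothing in the text makes sites do it, however.

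**The existing rules are soft.** Both say should, so the contrast is between a recommendation and silence, not between a requirement and an exemption. This also stands.

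**The bias is hypothetical.** No document figure supports any of the shifts, and the smallest ones barely move the error rate. This is correct, which is why the table includes the low end.

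**A reader might go further and infer that nothing keeps patients blind, so that the self-rated VAS is compromised as well.** The documents do not support that. Cryoanalgesia is given during surgery under general anesthesia, no section says that patients are told their arm, and the synopsis label may be meant to include them. The consent pages are not in the available text and some of the procedure text is redacted, so a statement on patient blinding there cannot be ruled out. What can be said is narrower: the visible sections never say who the label covers.

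**The study calls itself exploratory (section 9.6).** That limits how serious the point is, but the change costs so little that it is still worth making.

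**Conclusion.** The point holds as a gap in the plan. Section 7.11 gives no blinded-tester rule for spirometry or ambulatory movement, although it gives one for VAS and for allodynia testing, and FEV1 at 48 hours is a co-primary endpoint. The synopsis label does not fill the gap because it does not say who is blinded.

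The size of any resulting bias is unknown. Under the assumed shifts the effect on the FEV1 test runs from negligible (5.6% at 0.02 L) to serious (about 30% at 0.13 L, half the planned difference). The conclusion rests on two premises from outside the documents: that spirometry results respond to coaching and effort, and that any influence would run in one direction.

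The change should be made. The omission contradicts no figure in the plan, and it does not show that FEV1 will be collected unblinded or that patients will know their arm.

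**What to change.** 1. In the spirometry and ambulatory movement paragraphs of section 7.11, state that the blinded tester who collects VAS also performs these assessments at the 48, 72, 96 and 120 hour visits and at discharge.
2. State that the operator for the 30-day spirometry is also blinded. That visit has no VAS, so a blinded person has to be named for it.
3. In the synopsis and section 4.1, say who the blinded label covers. If it is meant to include patients, state that the arm is withheld from them through the 180-day allodynia screening. Stopping at discharge would be too early, because patients' answers at 90 and 180 days decide who is asked to come in for the allodynia test.
4. Optionally, record the patient's guess of allocation. It would be hard to interpret, because section 10.0 lists numbness around the incision as a possible symptom and some patients may infer their arm from it.

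The cost is protocol wording, a small scheduling burden in hospital and a blinded operator at 30 days. No visits are added and the sample size does not change.

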8.0 DATA MANAGEMENT AND INTEGRITY

8.1 Data Completion and Record Keeping

8.1.1 Source Documents

Source documents are documents on which information regarding subjects are first recorded. PI subject files or hospital records generally are the basis of source document information. This may include but is not limited to, original subject files, hospital/clinic records, original recordings/tracing, digital images from automated instruments, X-ray films, and laboratory results.

Source documents must be retained by the PI as part of the subject's permanent medical record. The information in the source documents is used to complete the eCRFs. All information captured on the eCRFs should be completely and accurately supported in source documentation. Study Monitors will verify data reported on eCRFs with site source documents. Any additional information relevant to the study should be included in the source documents. In particular, any deviations from the study protocol or procedures should be recorded in the source documents. The PI will retain originals of all source documents, subject consent forms, and study data.

8.1.2 Data Collection

An EDC system will be utilized by study site personnel to transfer study data from source records (medical records and/or source document worksheets) onto common eCRFs. This system is a web-based,

secure electronic software application. This system is designed, developed, and maintained in a manner that is compliant with national and international GCP data protection/data privacy and electronic record/electronic signature (e.g., 21 CFR Part 11) regulatory requirements. The platform software has been validated in accordance with 21 CFR Part 11, European Commission's Directive on Data Protection and US Safe Harbor Certification. Prior to being released for data entry, validation of the study level components (i.e. data entry screens, associated edit checks and work flow) will be conducted in accordance with approved user acceptance testing procedures. Access to this system will be controlled so that only authorized users will have the ability to enter into the system. The system is considered a closed system according to 21 CFR Part 11 Electronic Records; Electronic Signatures.

The EDC system will be used to facilitate the collection of all study data at the site. Designated site personnel will be responsible for entering subject data into the EDC system. All external and Sponsor internal users will be trained on the EDC application at a level dependent on their planned function.

An EDC digital User Manual will be available under the help menu within the EDC website to assist in the collection and entry of source data into the electronic casebook.

Investigative study sites will be asked to enter subject data into the eCRFs no later than 2 weeks from the time the subject was seen for their scheduled study visit.

Detailed description of the eCRF components are included in the eCRF Completion Instructions. These will be provided to the Investigators prior to initiating subject enrollment. The respective eCRFs must be fully completed for each subject and signed electronically.

Data collected during the clinical investigation for each subject will be maintained as accurately and completely as possible with entries into an electronic data capture system provided by AtriCure. The personal data recorded on all documents, including copy documents, and within the system will be regarded as confidential. The Investigator will be responsible for the timing, completeness and accuracy of the details entered within the electronic data capture system. All data entered in the database must have source documents in the subject's medical records.

Data will be entered into the electronic data capture system by members of the Investigational team who have received training in the use of the system. The system will generate data queries at the point of data entry based on validation checks defined by AtriCure. Such validation checks will primarily be focused on validation of key variables including selected subject demographics, appropriate value ranges and date checks. Resolution of the queries will be the responsibility of the Clinical Investigator and investigation team members. Following completion of all data queries on each eCRF, the Clinical Investigator will be responsible for reviewing and confirming agreement to the data within the system.

The Investigator must record the subject's participation in this clinical investigation in the subject's hospital notes. In addition, the Investigator must keep a separate list of all subjects entered into this clinical investigation showing each subject's name, date of birth and assigned subject number (for identification purposes). A subject Identification Log will be provided in the Investigator's File for this purpose.

8.1.3 Data Correction

Corrections to eCRFs will be prompted via automated electronic edit checks and queries manually created by reviewers. The corrections and the individual making the correction(s) to the eCRF will be within EDC.

8.1.4 Investigator Regulatory Binder

Each Investigator must maintain an accurate, complete, and current copy of the Investigator Regulatory Binder. Upon receipt of copies of changes or revision updates to the Binder from the Sponsor, the Investigator will add the updated document to the Regulatory Binder. If an Investigator holds multiple copies of the Regulatory Binder, then all copies must be updated with the current revisions.

8.1.5 Study Correspondence

Each Investigator and all personnel from the investigational site will maintain records of all correspondence, electronic, written, and verbal, relating to any aspect of the clinical investigation. The records are maintained in the Investigator regulatory Binder consisting of, but not limited to correspondence with other participating clinical investigators, the reviewing IRB, and the Sponsor. The CRA will examine the contents of the correspondence.

8.1.6 Data Privacy

Subjects will be made aware that their personal data will be collected and processed in accordance with data protection legislation including the Health Insurance Portability and Accountability Act of 1996 (HIPAA). Subjects will be asked to sign an Authorization for Release of Personal Health Information (PHI) for the purpose of this investigation. This authorization may be combined with the ICF depending on local IRB preference. Results from the Clinical Investigation may be published. However, subject confidentiality will be maintained at all times and it will not be possible to identify individual subjects from any data presented.

8.1.7 Record Retention, Inspection, and Custody

The PI must maintain all documentation related to the study until notified by the Sponsor. The PI will allow representatives of the Sponsor, IRB, the FDA, or other government regulatory agencies to inspect all study records, eCRFs, and corresponding portions of the subject's office and/or hospital medical records at regular intervals during the study. These inspections are to verify adherence to the protocol, integrity of the data being captured on the eCRFs, and compliance with applicable regulations.

Subject medical records will be kept confidential. Study reports will not identify subjects by name. These reports may be submitted to the FDA and/or regulatory authorities.

If custody of the records is transferred, notice of such a transfer should be given to the Sponsor no later than ten (10) working days after the transfer occurs.

The Investigator should retain copies of all documents pertaining to this clinical investigation (including source documentation, the informed consent document and any other documents to identify the subjects) for at least 2 years after this clinical investigation is completed. In addition, if the Clinical Investigator moves/retires, etc., he/she should provide AtriCure Inc. the name and address of the person who will look after and be responsible for the subjects' clinical investigation related records.

